13. ETHICS

13.1. Institutional Review Board (IRB)/Ethics Committee (EC)

It is the responsibility of the investigator to have prospective approval of the study protocol, protocol amendments, informed consent/assent documents, and other relevant documents, eg, recruitment advertisements, if applicable, from the IRB/EC. All correspondence with the IRB/EC should be retained in the investigator file. Copies of IRB/EC approvals should be forwarded to Pfizer.

The only circumstance in which an amendment may be initiated prior to IRB/EC approval is where the change is necessary to eliminate apparent immediate hazards to the subjects. In that event, the investigator must notify the IRB/EC and Pfizer in writing immediately after the implementation.

13.2. Ethical Conduct of the Study

The study will be conducted in accordance with legal and regulatory requirements, as well as the general principles set forth in the International Ethical Guidelines for Biomedical Research Involving Human Subjects (Council for International Organizations of Medical Sciences [CIOMS] 2002), Guidelines for GCP (ICH 1996), and the Declaration of Helsinki (World Medical Association 1996 and 2008).

In addition, the study will be conducted in accordance with the protocol, the ICH guideline on GCP, and applicable local regulatory requirements and laws.

13.3. Subject Information and Consent

All parties will ensure protection of subject personal data and will not include subject names or other identifiable data in any reports, publications, or other disclosures, except where required by law.

When study data are compiled for transfer to Pfizer and other authorized parties, subject names, addresses, and other identifiable data will be replaced by a numerical code consisting of a numbering system provided by Pfizer in order to de-identify study subjects. The study site will maintain a confidential list of subjects who participated in the study linking their numerical code to the subject's actual identity. In case of data transfer, Pfizer will maintain high standards of confidentiality and protection of subject personal data consistent with applicable privacy laws.

The informed consent/assent documents must be in compliance with ICH GCP, local regulatory requirements, and legal requirements, including applicable privacy laws.

The informed consent/assent documents used during the informed consent process must be reviewed by the sponsor, approved by the IRB/EC before use, and available for inspection.

In addition, a study-specific assent form will be provided to the subjects, as required by local regulations, who have not yet reached the legal age of majority. It is to be understood as the child's will to participate in a study after having received age-appropriate information and is sometimes also referred to as "knowing agreement."

The investigator must ensure that each study subject, or his or her legally acceptable representative, or parent(s) or legal guardian if a minor, is fully informed about the nature and objectives of the study and possible risks associated with participation.

Whenever consent is obtained from a subject's legally acceptable representative/parent(s) or legal guardian, the subject's assent (affirmative agreement) must subsequently be obtained when the subject has the capacity to provide assent, as determined by the IRB/EC. If the investigator determines that a subject's decisional capacity is so limited he/she cannot reasonably be consulted, as permitted by the IRB/EC and consistent with local regulatory and legal requirements, then the subject's assent may be waived with source documentation of the reason assent was not obtained. If the study subject does not provide his/her own consent, the source documents must record why the subject did not provide consent (eg, minor, decisionally impaired adult), how the investigator determined that the person signing the consent was the subject's legally acceptable representative, the consent signer's relationship to the study subject (eg, parent, spouse), and that the subject's assent was obtained, or waived. If assent is obtained verbally, it must be documented in the source documents.

If the study includes minor subjects who reach the age of majority during the study, as recognized under local law, they must be re-consented as adults to remain in the study. If the enrollment of "emancipated minors" is permitted by the study age criteria, the IRB/EC, and local law, they must provide documentation of legal status to give consent without the permission of a parent or legal guardian.

The investigator, or a person designated by the investigator, will obtain written informed consent from each subject or the subject's legally acceptable representative, parent(s), or legal guardian and the subject's assent, when applicable, before any study-specific activity is performed, unless a waiver of informed consent has been granted by an IRB/EC. The investigator will retain the original of each subject's signed consent/assent document.

13.4. Subject Recruitment

Subject recruitment efforts are not required for this study because, as of protocol amendment 3, all subjects have been enrolled.

13.5. Reporting of Safety Issues and Serious Breaches of the Protocol or ICH GCP

In the event of any prohibition or restriction imposed (ie, clinical hold) by an applicable competent authority in any area of the world, or if the investigator is aware of any new information that might influence the evaluation of the benefits and risks of the investigational product, Pfizer should be informed immediately.

In addition, the investigator will inform Pfizer immediately of any urgent safety measures taken by the investigator to protect the study subjects against any immediate hazard, and of any serious breaches of this protocol or of ICH GCP that the investigator becomes aware of.

14. DEFINITION OF END OF TRIAL

14.1. End of Trial in a Member State

End of trial in a Member State of the European Union is defined as the time at which it is deemed that a sufficient number of subjects have been recruited and completed the study as stated in the regulatory application (ie, clinical trial application [CTA]) and ethics application in the Member State. Poor recruitment (recruiting less than the anticipated number in the CTA) by a Member State is not a reason for premature termination but is considered a normal conclusion to the study in that Member State.

14.2. End of Trial in All Other Participating Countries

End of trial in all other participating countries is defined as the end of the clinical phase of the study, which will be 48 hours after the last study visit (Visit 11) for the last subject (LSLV). At this time, sites will be closed out, the IRB/EC will be informed, and no further CIOMS reports will be sent.

15. SPONSOR DISCONTINUATION CRITERIA

Premature termination of this study may occur because of a regulatory authority decision, change in opinion of the IRB/EC, drug safety problems, or at the discretion of Pfizer. In addition, Pfizer retains the right to discontinue development of bivalent rLP2086 at any time.

If a study is prematurely terminated or discontinued, Pfizer will promptly notify the investigator. After notification, the investigator must contact all participating subjects and the hospital pharmacy (if applicable) immediately. As directed by Pfizer, all study materials must be collected and all CRFs completed to the greatest extent possible.

16. PUBLICATION OF STUDY RESULTS

16.1. Communication of Results by Pfizer

Pfizer fulfills its commitment to publicly disclose clinical trial results through posting the results of studies on www.clinicaltrials.gov (ClinicalTrials.gov), the European Clinical Trials Database (EudraCT), and/or www.pfizer.com, and other public registries in accordance with applicable local laws/regulations.

In all cases, study results are reported by Pfizer in an objective, accurate, balanced, and complete manner and are reported regardless of the outcome of the study or the country in which the study was conducted.

www.clinicaltrials.gov

Pfizer posts clinical trial US Basic Results on www.clinicaltrials.gov for Pfizer-sponsored interventional studies (conducted in patients) that evaluate the safety and/or efficacy of a Pfizer product, regardless of the geographical location in which the study is conducted. US Basic Results are submitted for posting within 1 year of the primary completion date for studies in adult populations or within 6 months of the primary completion date for studies in pediatric populations.

Primary completion date is defined as the date that the final subject was examined or received an intervention for the purposes of final collection of data for the primary outcome, whether the clinical study concluded according to the prespecified protocol or was terminated.

EudraCT

Pfizer posts EU Basic Results on EudraCT for all Pfizer-sponsored interventional studies that are in scope of EU requirements. EU Basic Results are submitted for posting within 1 year of the primary completion date for studies in adult populations or within 6 months of the primary completion date for studies in pediatric populations.

www.pfizer.com

Pfizer posts Public Disclosure Synopses (clinical study report synopses in which any data that could be used to identify individual patients has been removed) on www.pfizer.com for Pfizer-sponsored interventional studies at the same time the US Basic Results document is posted to www.clinicaltrials.gov.

16.2. Publications by Investigators

Pfizer has no objection to publication by an investigator of any information collected or generated by the investigator, whether or not the results are favorable to the investigational vaccine. However, to ensure against inadvertent disclosure of confidential information or unprotected inventions, the investigator will provide Pfizer an opportunity to review any proposed publication or other type of disclosure before it is submitted or otherwise disclosed.

The investigator will provide manuscripts, abstracts, or the full text of any other intended disclosure (poster presentation, invited speaker or guest lecturer presentation, etc) to Pfizer at least 30 days before they are submitted for publication or otherwise disclosed. If any patent action is required to protect intellectual property rights, the investigator agrees to delay the disclosure for a period not to exceed an additional 60 days.

The investigator will, on request, remove any previously undisclosed confidential information (other than the study results themselves) before disclosure.

If the study is part of a multicenter study, the investigator agrees that the first publication is to be a joint publication covering all centers. However, if a joint manuscript has not been submitted for publication within 12 months of completion or termination of the study at all participating sites, the investigator is free to publish separately, subject to the other requirements of this section.

For all publications relating to the study, the institution will comply with recognized ethical standards concerning publications and authorship, including Section II - "Ethical Considerations in the Conduct and Reporting of Research" of the Uniform Requirements for Manuscripts Submitted to Biomedical Journals, <http://www.icmje.org/index.html#authorship>, established by the International Committee of Medical Journal Editors.

Publication of study results is also provided for in the CSA between Pfizer and the institution. In this section entitled Publications by Investigators, the defined terms shall have the meanings given to them in the CSA.

RCDC	reverse cumulative distribution curve
rLP2086	recombinant lipoprotein 2086
RRI	research-related injuries
SAE	serious adverse event
SAP	statistical analysis plan

1. AMENDMENTS FROM PREVIOUS VERSION(S)

Version	Date	Summary of Changes/Comments
Version 1.0	March 5 th 2012	Initial Version for Final Protocol Dated 14 December 2011 (05Jan2012 in GDMS)
Version 2.0	January 17 th , 2014	Amended version for Protocol Amendment 2
Version 3.0	June 1, 2015	Amended version for Protocol Amendment 3
Version 4.0	June 5, 2017	Amended version for Protocol Amendment 4
Version 4.1	October 25, 2017	Amended version to clarify the language for mITT population in section 5.5. Removed the requirement for the creation of randomization listing in section 8.2.5.1

2. INTRODUCTION

The purpose of this document is to provide further details about the statistical analysis methods specified in the study protocol B1971033. This study is sponsored by Pfizer. A brief description of the study design and the study objectives are given. Subsequent sections include analysis populations, and the definitions of endpoints, followed by details about statistical methods. The list of tables/figures/listings, mock-up tables, listings, figures, and programming rules are prepared separately based on the methods described in this document. Any major deviations from the methods specified in this document and the protocol must be discussed in the clinical study report.

This SAP version is updated to reflect changes made in Protocol Amendment 4, dated April 18, 2017. Endpoints and analyses relating to the extension of the Booster Stage from 12 months to 26 months postbooster vaccination are specified. Subjects from primary study B1971012, Group 2 (0, 2, 6-schedule) and Group 3 (0, 6-schedule) will proceed to the 26 months postbooster vaccination visit.

In this document, text taken directly from the protocol has been italicized.

2.1. Study Design

This study consists of two stages. Stage 1 is a long-term serologic assessment in subjects enrolled in previously conducted Pfizer studies using the final formulation and dose of bivalent rLP2086 (primary studies). Subjects will attend up to 6 study visits (through 48 months after receiving last dose of investigational product) for collection of a 20-mL blood sample at each of these visits to evaluate the immunogenicity across the time. Protocol Amendment 3 added the Booster Stage in which a booster vaccination with a single dose of bivalent rLP2086 will be administered, plus two additional blood draws. To further evaluate the safety and immunogenic response to booster vaccination, Protocol Amendment 4 extended the Booster Stage from 12 months to 26 months following the booster dose. Subjects from primary study B1971012, Group 2 (0, 2, 6-schedule) and Group 3 (0, 6-schedule) will proceed to the 26 months postbooster vaccination visit.

An overview of the study design is provided in [Table 1](#).

Table 1. Overview of Study Design

	STAGE 1						BOOSTER STAGE				
Visit purpose	Blood draw	Booster vaccination	Blood draw	6-Month telephone call	Blood draw	Blood draw					
Visit number	1	2	3	4	5	6	7	8	9	10	11
Approximate month	6	12	18	24	36	48	48	1 Month after booster	6 Months after booster	12 Months after booster	26 Months after booster
Vaccination							Bivalent rLP2086				
Blood draw	20 mL		20 mL		20 mL	20 mL					

2.2. Study Objectives

The primary objective of Stage 1 of this study is to describe the immunogenicity of bivalent rLP2086 as determined by hSBA-titers to 4 primary test strains at approximately 6, 12, 18, 24, 36, and 48 months after the last dose (second or third dose) of bivalent rLP2086 in the ‘primary’ study (a previously conducted Pfizer study using the final formulation and dose of bivalent rLP2086).

The primary objective of the Booster Stage of this study is to describe the immune response as measured by hSBA titers to 4 primary test strains 1 month following the last vaccination with bivalent rLP2086 in the primary study, before the booster vaccination, and 1 month, 12 months, and 26 months after a single booster dose of bivalent rLP2086.

The primary safety objective is to evaluate the safety profile of bivalent rLP2086 as measured by the incidence of local reactions, systemic events, AEs, serious adverse events (SAEs), newly diagnosed chronic medical conditions (NDCMCs), medically attended events, and immediate AEs following a booster vaccination of bivalent rLP2086.

CCI

3. INTERIM ANALYSES, FINAL ANALYSES AND UNBLINDING

Because of the timing of enrollment into the primary studies, subjects will reach the booster stage of Study B1971033 over an extended period. Up to three (3) analyses of the study will be conducted.

The first interim analysis will occur when all subjects who participated in the B1971012 primary study have Visit 8 (1 month after the booster vaccination) immunogenicity data available. The analysis will include all data from visits 1 through 8, for B1971012 subjects only (including data from visits 1 through 6 for any B1971012 subjects who did not receive the booster dose).

A second interim analysis *will* be conducted, when all subjects who participated in the B1971012 primary study, Group 3 (0, 6-schedule) have Visit 10 (12 months after the booster vaccination) immunogenicity data available. The analysis will include all data from visits 1 through 10, for B1971012 subjects only (including data from visits 1 through 6 for any B1971012 subjects who did not receive the booster dose).

The final analysis will be conducted once all immunogenicity data for all subjects enrolled in B1971033 are available, from all primary studies B1971010, B1971012 and B1971015. This includes data from visits 1 through 6 for any subject who did not receive the booster dose.

These criteria for analysis relate to primary strain immunogenicity data only. CCI [REDACTED]

Information from interim analyses will be used for internal decision making on further development of the vaccine, and will not modify the current study. Since the study is descriptive, there will be no type I error impact for these interim analyses.

Unblinding is not applicable to this study as the booster vaccination phase is open-label.

4. HYPOTHESES AND DECISION RULES

This Section is not applicable as it is a descriptive study and no hypothesis is tested.

5. ANALYSIS SETS

5.1. Full Analysis Set

The full analysis set will be the ‘As Enrolled’ population, which will include all of the subjects enrolled in this study.

5.2. Immunogenicity Analysis Set

Only subjects who were compliant with primary study eligibility criteria while enrolled in the primary study will be included in this study. Therefore, the modified intent-to-treat (mITT) population will be used for Stage 1 immunogenicity analyses. The mITT population will include subjects who have at least 1 valid and determinate assay result in Stage 1 of Study B1971033.

For booster stage time points, the primary immunogenicity analysis will be based on the evaluable population. For analyses including the 26 months postbooster vaccination time point, the analyses will use the subset of evaluable population for Booster stage who proceed to Visit 11.

The evaluable population includes subjects who:

[REDACTED]

1. Are eligible for the study (i.e., meet all Stage 1 and Booster Stage eligibility criteria).
2. Have received the scheduled investigational product as intended.
3. Have a prevaccination blood drawn prior to the booster vaccination, and have a postvaccination blood draw within 28-42 days after the booster vaccination.
4. Have valid and determinate assay result for the proposed analysis.
5. Have received no prohibited vaccines or treatment.
6. Have no other major protocol violations as determined by the sponsor's global medical monitor.

For above listed items, 1 through 4 will be computerized checks of the data, while items 5 and 6 will be determined by clinical review. A major protocol violation is a protocol violation that, in the opinion of the sponsor's global medical monitor would materially affect assessment of immunogenicity, e.g, subject receipt of a prohibited vaccine or medication that might affect immune response or a medication error with suspected decrease in potency of the vaccine. The global medical monitor from the sponsor will identify those subjects with protocol violations before any immunogenicity analysis is carried out.

Booster stage immunogenicity analyses will also be performed for the mITT population, which will include subjects who received the booster vaccination and who have at least 1 valid and determinate assay result in the booster stage. For analyses including the 26 months postbooster vaccination time point, the analyses will use the subset of mITT population for Booster stage who proceed to Visit 11.

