Visit Window	48 Months After Last Dose of Bivalent rLP2086 in Primary Study^a (1396-1484 Days After Last Dose of Bivalent rLP2086, and Within 42 Days After Visit 6)	1 Month After Booster (28-42 Days After Visit 7)	6 Months After Booster (168 to 196 Days After Visit 7)	12 Months After Booster (330-390 Days After Visit 7)	26 Months After Booster (750-810 Days After Visit 7)
Collect e-diary		X			
Record use of antipyretic medication in the e-diary	Day 1 to 7				
Assess reactogenicity	Day 1 to 7				
Provide the subject with a memory aid		X			
Complete study visit/AE checklist	X	X	X	X	X
(S)AE collection appropriate for the visit ^h	X	X	X	X	X

- a. Visit 7 may occur a maximum of 42 days after Visit 6.
- b. If a subject reaches the age at which he or she is able to provide legal consent during the study, the subject’s consent must be obtained.
- c. Subjects must satisfy all eligibility criteria for Stage 1 and the booster stage. In addition, subjects participating in Visit 11 must meet eligibility criteria for Visit 11.
- d. Vital signs will include blood pressure, pulse rate, and temperature (oral).
- e. If Visits 6 and 7 do not occur on the same day, ensure that vital sign measurements and recording of nonstudy vaccinations are performed again at Visit 7.
- f. Nonstudy vaccination occurring from the final blood draw in the primary study until Visit 11. From Visit 7, this also includes allergen immunotherapy.
- g. Amount of blood collected is approximately 20 mL.
- h. Subject or subject’s parent(s)/legal guardian to report any AEs within 48 hours following Visit 10 and Visit 11.

Abbreviations: AE = adverse event; e-diary = electronic diary; IVRS = interactive voice response system; RRI = research-related injury; SAE = serious adverse event.

Table 3. Adverse Event Reporting Schedule

Stage 1							Booster Stage				
AE Type	Visit 1	Visit 2	Visit 3	Visit 4	Visit 5	Visit 6	Visit 7	Visit 8	Visit 9	Visit 10	Visit 11
SAE ^a	Nonactive reporting of SAEs to the primary study						From booster stage ICD to Visit 9			Nonactive reporting of SAEs to the B1971033 study	
NDCMC ^b	From 6-month telephone call in the primary study to Visit 11										
MAE							From booster stage ICD to Visit 9				
RRI ^c	48 Hours after blood draw	48 Hours after blood draw	48 Hours after blood draw	48 Hours after blood draw	48 Hours after blood draw	48 Hours after blood draw				48 Hours after blood draw	48 Hours after blood draw

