9.3. Immunogenicity Analysis Populations

Only subjects who were compliant with primary study eligibility criteria while enrolled in the primary study will be included in this study. Therefore, the modified intent-to-treat (mITT) population will be used for Stage 1 immunogenicity analyses. The Stage 1 mITT population will include subjects who have at least 1 valid and determinate assay result in Stage 1 of Study B1971033.

In general, the evaluable population will include all subjects who were eligible, received all investigational products, had blood drawn for assay testing within the required time frames, had valid and determinate assay results for the proposed analysis, and had no important protocol deviations. A major protocol deviation is one that, in the opinion of the sponsor's global medical monitor, would materially affect assessment of immunogenicity, eg, subject receipt of a prohibited vaccine or medication that might affect immune response or a medication error with suspected decrease in potency of the vaccine. For booster stage time points (Visits 7, 8, 10, and 11), the primary immunogenicity analysis will be based on the evaluable population (for summaries including Visit 11 for the subset of subjects of the evaluable population who participated in Visit 11). Booster stage immunogenicity analyses will also be performed for the booster stage mITT population (for summaries including Visit 11 for the subset of subjects of the booster stage mITT population who participated in Visit 11), which will include subjects who received the booster vaccination and who have at least 1 valid and determinate assay result.

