8.2. Statistical Analyses

8.2.1. Analysis of Primary Endpoints

The immunogenicity data will be analyzed within each primary study. The primary analysis will include the summary tables on the primary immunogenicity endpoint (proportion of subjects with hSBA titer \geq LLOQ) at each blood sampling timepoint in the primary analysis populations (mITT for Stage 1, evaluable population for Booster Stage at Visits 8 and 10) for each of the 4 primary test strains.

The analysis for immunogenicity endpoints including Visit 11 will use the subset of evaluable population for Booster stage subjects who proceed to Visit 11.

CCI [REDACTED]

CCI [REDACTED]

[REDACTED]

[REDACTED]

CCI

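### SAP 5.2 checks only the Visit 8 draw window, so by default off-window Visit 10 and 11 draws enter primary booster estimates that Protocol 9.3 generally restricts to on-time draws

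*SAP*

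**What the plan says.** Protocol 9.3 describes the evaluable population, in general terms, as subjects who among other things "had blood drawn for assay testing within the required time frames". It then gives that population its role: "For booster stage time points (Visits 7, 8, 10, and 11), the primary immunogenicity analysis will be based on the evaluable population". Summaries that include Visit 11 use those evaluable subjects who took part in that visit.

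Protocol Table 2 gives each post-booster blood draw its own window, and Protocol 6.3.2, 6.3.4 and 6.3.5 repeat them. Visit 8 is 28-42 days after Visit 7. The column heads for the later draws read, up to the closing bracket, "12 Months After Booster (330-390 Days After Visit 7" and "26 Months After Booster (750-810 Days After Visit 7".

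SAP 5.2 turns the evaluable population into six numbered criteria. Item 3 is the only one about draw timing: "Have a prevaccination blood drawn prior to the booster vaccination, and have a postvaccination blood draw within 28-42 days after the booster vaccination". Item 4 asks for a usable assay result. Item 6 excludes other major violations as judged by the medical monitor. On how the items are applied, the SAP says that "1 through 4 will be computerized checks of the data, while items 5 and 6 will be determined by clinical review".

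SAP 8.2.1 then names the primary set as the "evaluable population for Booster Stage at Visits 8 and 10". For endpoints that include Visit 11, the analysis "will use the subset of evaluable population for Booster stage subjects who proceed to Visit 11".

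**The concern.** The SAP uses one evaluable population for three post-booster time points but checks the draw date for only one of them. The 12- and 26-month proportions describe how long the response lasts, so time since the booster is part of what they estimate. A 12-month figure that includes draws taken well before or after 12 months describes something slightly different from its label.

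There is also a reproducibility problem. A programmer who applies Protocol 9.3 with the Table 2 windows and one who applies SAP 5.2 as printed could obtain different denominators for the same primary endpoint. No hypothesis is tested, so type I error is not at stake. What is at stake is which samples enter the primary estimates.

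**Working it through.** **Step 1: windows against checks.**

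| Draw | Protocol Table 2 window (days after Visit 7) | Window in SAP 5.2 item 3 | Primary set |
|---|---|---|---|
| Visit 8 | 28-42 | 28-42 | evaluable |
| Visit 10 | 330-390 | none | evaluable |
| Visit 11 | 750-810 | none | evaluable, Visit 11 subset |

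The 330-390 and 750-810 day windows appear nowhere in the visible SAP.

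**Step 2: does another SAP rule apply the later windows?**

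- Item 4 concerns the assay result, not the draw date.
- The Visit 11 subset is defined by who goes on to that visit, not by the day of the draw.
- Item 6 could remove a subject, but by clinical judgement. Its examples are prohibited products and vaccine-potency errors. SAP 5.6.2 has the deviation list compiled before database closure for the first interim analysis, which by SAP 3 covers Visits 1 to 8 in B1971012 subjects. No later update for Visit 10 or 11 draws is stated.
- SAP 8.2.5.1 counts samples inside, before and after the time frame, so off-window draws are foreseen. It removes none.
- The booster mITT analysis has no draw window, so it gives no window-compliant estimate either.

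By default, then, an off-window Visit 10 or 11 draw stays in unless item 6 is used.

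**Step 3: size.** The plan states no figure on this point, so there is nothing to reproduce. The only inputs from the documents are the windows and the estimate of up to 200 subjects at Visit 11. Everything else here is assumed.

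The window centres are day (28+42)/2 = 35, (330+390)/2 = 360 and (750+810)/2 = 780. The gaps are 360 − 35 = 325 and 780 − 360 = 420 days. Assume that the response proportion falls linearly between adjacent visits and that all off-window draws lie on one side. Then

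shift in the 12-month proportion = off-window share × fall between visits × days from day 360 / gap.

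The assumed ranges are a share of 5-20%, a fall of 10-30 points and draws 60-180 days from the centre.

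| Case | Late draws (estimate too low) | Early draws (estimate too high) |
|---|---|---|
| Low | 0.05 × 10 × 60/420 = 0.07 | 0.05 × 10 × 60/325 = 0.09 |
| Middle | 0.10 × 20 × 90/420 = 0.43 | 0.10 × 20 × 90/325 = 0.55 |
| High | 0.20 × 30 × 180/420 = 2.57 | 0.20 × 30 × 180/325 = 3.32 |

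All results are in percentage points. If the middle case's 10% is split evenly between early and late, the net shift is 0.05 × 20 × 90/325 − 0.05 × 20 × 90/420 = 0.28 − 0.21 = 0.07 points (0.06 before rounding).

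For Visit 11, a cruder form is share × difference in response between off-window and in-window draws. With a share of 5-20% and a difference of 5-20 points, this gives 0.05 × 5 = 0.25 to 0.20 × 20 = 4.0 points.

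**Step 4: precision lost by applying the window.** Take 200 subjects at Visit 11 and an assumed 80% response. The exact 95% interval is 73.8-85.3%. Removing 5%, 10% or 20% of draws leaves 190, 180 or 160 subjects, with intervals of 73.6-85.4%, 73.4-85.6% and 73.0-85.9%.

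**The case against.** The strongest reply is that the SAP is allowed to be the operative definition. Protocol 9.3 speaks in general terms and does not spell out which time frames it means. Protocol 9 leaves detailed methods to the SAP and lets it modify the plan. The SAP's structure is also coherent: evaluability is fixed by the pre-booster and 1-month draws, and that cohort is then followed. Protocol 9.3 itself defines the Visit 11 subset by participation, and the Stage 1 persistence analysis uses mITT with no draw window in either document. Programming rules are kept separately (SAP 2) and might handle visit windows. A redacted line also precedes the SAP's list of criteria.

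Part of this stands. Reading the required time frames as the Table 2 windows is an inference, though a natural one, since those are the windows the protocol sets for these draws. A reader might infer that the SAP deliberately overrides the protocol. The documents do not support that, because the SAP nowhere presents the single window as a change. Whether it would count as a major modification needing both documents is arguable, and the point does not rest on it. The separate programming rules are unseen and cannot be credited, and the six visible criteria read as a complete set.

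A reader might also infer that off-window draws must stay in the primary estimates. That goes too far: the item 6 examples are not exhaustive, and the medical monitor could exclude such subjects.

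A third tempting reading is that the plan leaves open what happens to later samples when the Visit 8 draw is missed or off-window. It does not. Item 3 makes that subject non-evaluable, so the later samples are outside the primary sets for Visits 10 and 11.

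**Conclusion.** The mismatch is real and should be fixed. The protocol's general rule requires timely draws at every booster time point, whereas the SAP's computerized rule enforces this only at Visit 8. Off-window 12- and 26-month draws therefore enter the primary estimates unless someone decides otherwise case by case.

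The documents do not support a claim of material bias. They give no off-window rate, and every share, fall, draw day and the linear decline above is assumed. The middle case, 0.43 points too low or 0.55 too high, is small beside an interval half-width of about (85.3 − 73.8)/2 = 5.75 points in the Visit 11 illustration. The high cases need 20% of draws to lie 180 days from the window centre, all on one side. The main gain from the change is an unambiguous primary set.

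**What to change.** In SAP 5.2 item 3, and by reference in 8.2.1, add two computerized checks. A Visit 10 draw must fall 330-390 days after Visit 7, and a Visit 11 draw 750-810 days after Visit 7, to count in that time point's primary estimate. Keep off-window draws in the booster mITT analysis. State that the check works per time point, because Protocol 9.3 could also be read as removing the whole subject for one late draw.

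If the sponsor intends only the Visit 8 window to define evaluability, state that in both Protocol 9.3 and the SAP.

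The first option costs SAP wording and two flags, with no new data. Its downside is slightly smaller denominators that differ between time points. The second option costs a wording change in both documents and leaves the timing of the 12- and 26-month draws uncontrolled in the primary analysis.
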